4.3.1. GSK3640254 Oral Dose (Treatment Periods 1 and 2)

The oral GSK3640254 dose is within the therapeutic range for the treatment of HIV. The 200 mg dose is lower than the highest once-daily dose (320 mg QD) in the first time in human (FTIH) study 207187. In Study 207187 (single Ascending Dose [SAD]/ multiple Ascending Dose [MAD]), doses up to 200 mg QD for 14 days were well tolerated.

4.3.2. GSK3640254 Intravenous Dose (Treatment Period 1)

The dose of [¹⁴C]-GSK3640254 to be administered intravenously is a microdose of 100 µg, which will be infused over 1 h. A microdose was selected because GSK3640254 has not previously been administered by IV infusion to humans. That dose level meets the criterion for a microdose, for the following reasons:

- It is ≤ 100 µg.
- It is ≤ 1/100th of the lowest predicted pharmacologically-active oral dose in HIV-patients (i.e., 5 mg single, oral dose) based on a PK/PD model of GSK3532795 and the distribution of PBAEC90 obtained with GSK3640254 in in vitro experiment with 36 Gag/PR genotyped viruses (e.g. mean of 19.1 ng/mL with CV% of 33%).
- Predicted steady-state exposures for a higher 200 mg QD dose are essentially equal to the NOAEL exposure in a 4-week oral toxicity study in rats, although no NOAEL was identified in dogs for GI intolerability and minimal effects of parietal cells following 4 weeks of dosing. Predicted steady-state exposures over the proposed dose range along with fold cover to rat and dog lowest-observed-adverse-effect level (LOAEL) exposures, the lowest exposures where minimal, reversible effects on parietal and/or chief cells were identified.

To ensure clinically-relevant systemic exposure during the microdose, the IV infusion of [¹⁴C]-GSK3640254 will be administered with an oral non-radiolabelled dose of 200 mg GSK3640254.

The 100 µg microtracer dose administered as a 1-h IV infusion is projected (based on allometry) to achieve a GSK3640254 C_{max} ~3 ng/mL, which is >200-fold lower than the lowest observed geometric mean human C_{max} following a 200 mg dose (Study 207187). This dose can be categorised as a microdose and as such required safety cover is detailed in ICH M3 (R2).

4.3.3. Radiolabel Dose

The effective dose of radiolabelled drug administered in human mass balance studies is calculated from data on the distribution and elimination of the radioactive drug from laboratory animals, considering the nature of the isotope, the route of administration, the

concentration of radioactivity in individual tissues/organs and the residence or elimination half-life of the radioactivity from those tissues/organs.

4.3.4. Total Radiation Exposure

In this study, each participant will receive the following doses of radioactivity:

- approximately 3.7 kBq (100 nCi) in Treatment Period 1.
- approximately 3.15 MBq; (85 µCi) in Treatment Period 2.

The total amount of radiation exposure in the study is ~3.15 MBq; (~85.1 µCi).

It is estimated that the combined total effective dose for the two treatment periods will be <1 mSv. On this basis, the maximum administered activity would comply with the [ICRP](#), 1992 recommendation of a 1 mSv maximum for Category IIa projects (0.1 – 1 mSv ; minor risk), further details are in [Appendix 6](#).

4.4. End of Study Definition

A participant is considered to have completed the study if he has completed all phases of the study including the follow-up visit (end of study visit).

The end of the study is defined as the date of the last visit of the last participant in the study.

5. STUDY POPULATION

Prospective approval of protocol deviations to recruitment and enrolment criteria, also known as protocol waivers or exemptions, is not permitted.

5.1. Inclusion Criteria

Participants are eligible to be included in the study only if all the following criteria apply:

Age
1. Participant must be 30 to 50 years of age inclusive, at the time of signing the informed consent.

Type of Participant and Disease Characteristics
2. Participants who are overtly healthy as determined by medical evaluation including medical history, physical examination, laboratory tests, vital signs and ECG. A participant with a clinical abnormality or laboratory parameter (i.e. outside the reference range for the population being studied), which is not specifically listed in the eligibility criteria, may be included only if the investigator agrees and documents that the finding is unlikely to introduce additional risk factors and will not interfere with the study procedures.
3. History of regular bowel movements (averaging one or more bowel movements per day).
4. Non-smoker, or ex-smoker who hasn't regularly smoked for the 6 months before screening.

Weight
5. Body weight of 50 kg and above, and body mass index (BMI) within the range 19.0 to 31.0 kg/m ² (inclusive).

Sex
6. Male only. Male participants are eligible to participate if they agree to the following during the study, including washout periods: 
 • Refrain from donating sperm • And Either: 
 1) be abstinent from heterosexual intercourse as their preferred and usual lifestyle (abstinent on a long term and persistent basis) and agree to remain

abstinent

OR

2) Agree to use a male condom when having penile-vaginal intercourse with a woman of childbearing potential unless vasectomised.

Informed Consent

7. Capable of giving signed informed consent as described in Section 10.1 which includes compliance with the requirements and restrictions listed in the ICF and in this protocol.

5.2. Exclusion Criteria

Participants are excluded from the study if any of the following criteria apply:

Medical Conditions

1. Current or chronic history of liver disease, or known hepatic or biliary abnormalities (with the exception of Gilbert's syndrome or asymptomatic gallstones). Participants with a history of cholecystectomy must be excluded.
2. Significant history of or current cardiovascular, respiratory, hepatic, renal, gastrointestinal, endocrine, hematological, or neurological disorders capable of significantly altering the absorption, metabolism, or elimination of drugs; constituting a risk when taking the study intervention ; or interfering with the interpretation of data.
3. Any clinically relevant abnormality identified at the screening medical assessment (physical examination/medical history) clinical laboratory tests, or 12-lead ECG.
4. Current episode, recent history, or chronic history of diarrhoea.
5. Lymphoma, leukemia, or any malignancy within the past 5 years except for basal cell or squamous epithelial carcinomas of the skin that have been resected with no evidence of metastatic disease for 3 years.
6. Any history of significant underlying psychiatric disorder, including, but not limited to, schizophrenia, bipolar disorder with or without psychotic symptoms, other psychotic disorders, or schizotypal (personality) disorder.
7. Any history of major depressive disorder with or without suicidal features, or anxiety disorders that required medical intervention (pharmacologic or not) such as hospitalization or other inpatient treatment and/or chronic (>6 months) outpatient treatment. Participants with other conditions such as adjustment disorder or dysthymia that have required shorter term medical therapy (<6 months) without inpatient treatment and are currently well-controlled clinically or resolved may be considered for entry after discussion and agreement with the VH/GSK Medical

Monitor.

8. Any pre-existing physical or other psychiatric condition (including alcohol or drug abuse), which, in the opinion of the investigator (with or without psychiatric evaluation), could interfere with the participant's ability to comply with the dosing schedule and protocol
9. Regular use of known drugs of abuse or history of drug abuse or dependence within 6 months of the study.
10. Regular alcohol consumption within 6 months prior to the study defined as an average weekly intake of >21 units. One unit is equivalent to 8 g of alcohol: a glass (~240 mL) of beer, 1 small glass (~100 mL) of wine or 1 (~25 mL) measure of spirits.
11. History of or regular use of tobacco- or nicotine-containing products in the 3 months prior to screening.
12. Medical history of cardiac arrhythmias, prior myocardial infarction in the past 3 months, or cardiac disease or a family or personal history of long QT syndrome.
13. QTcF >450 msec

NOTES:

The QTc must be the QT interval corrected for heart rate according to Fridericia's formula (QTcF).

For purposes of data analysis, QTcF will be used as specified in the Reporting and Analysis Plan (RAP).

14. At Screening or prior to the first dose, a supine blood pressure (BP) that is persistently higher than 140/90 mmHg.
15. At Screening or prior to the first dose, a supine mean heart rate (HR) outside the range of 50–100 bpm. A heart rate from 100 to 110 bpm can be rechecked by electrocardiogram or vital signs within 30 minutes to verify eligibility.
16. A participant with known or suspected active COVID-19 infection OR contact with an individual with known COVID-19, within 14 days of study enrollment (WHO definitions Section 10.9.3.2)

Prior / Concomitant Therapy

17. Past or intended use of over-the-counter or prescription medication, including analgesics (eg, paracetamol), herbal medications, or grapefruit and Seville orange juices within 14 days prior to the first dose of study intervention until completion of the follow-up visit unless approved by the Investigator in conjunction with a ViiV Healthcare (VH)/GSK Medical monitor.
18. Treatment with any vaccine within 30 days prior to receiving study intervention.

Prior / Concurrent Clinical Study Experience

19. Current enrolment in a clinical trial; recent participation in a clinical trial and has received an investigational product within 3 months before the first dose in the current study.
20. Exposure to more than 4 new chemical entities within 12 months before the first dose in the current study.
21. Participation in a clinical trial involving administration of ¹⁴C-labelled compound(s) within the last 12 months. A participant's previous effective dose will be reviewed by the medical investigator to ensure there is no risk of contamination/carryover into the current study.
22. Received a total body radiation dose of greater than 10.0 mSv (upper limit of IRCP category II) or exposure to significant radiation (e.g., serial x-ray or computed tomography [CT] scans, barium meal, etc.) in the 3 years before this study.

Diagnostics Assessments

23. Alanine transaminase (ALT) $\geq 1.5x$ upper limit of normal (ULN). A single repeat of ALT is allowed within a single Screening period to determine eligibility.
24. Bilirubin $\geq 1.5x$ ULN (isolated bilirubin $\geq 1.5x$ ULN is acceptable if bilirubin is fractionated and direct bilirubin $< 35\%$). A single repeat of any laboratory abnormality is allowed within a single Screening period to determine eligibility.
25. Presence of Hepatitis B surface antigen (HBsAg) at screening or positive Hepatitis C antibody test result at screening or within 3 months before the first dose of study intervention AND positive on reflex to hepatitis C ribonucleic acid (RNA).
26. Positive HIV-1 and -2 antigen/antibody immunoassay at Screening.
27. Any positive (abnormal) response confirmed by the investigator or qualified designee-administered C-SSRS.
28. Any Grade 2 to 4 laboratory abnormality at Screening, with the exception of creatine phosphokinase (CPK) and lipid abnormalities (e.g., total cholesterol, triglycerides), and ALT (described above), will exclude a participant from the study unless the investigator can provide a compelling explanation for the laboratory result(s) and has the assent of the sponsor. A single repeat of any laboratory abnormality (other than a viral screening test for HIV-1/2, hepatitis B Virus [HBV], or hepatitis C Virus [HCV]) is allowed within a single Screening period to determine eligibility.
29. Any significant arrhythmia or ECG finding (e.g., prior myocardial infarction in the past 3 months, symptomatic bradycardia, non-sustained or sustained atrial arrhythmias, non-sustained or sustained ventricular tachycardia, second-degree atrioventricular block Mobitz Type II, third-degree atrioventricular block, complete heart block, or conduction abnormality) which, in the opinion of the investigator or VH/GSK Medical Monitor, will interfere with the safety for the individual

participant. Any acute laboratory abnormality at Screening which, in the opinion of the investigator, should preclude participation in the study of an investigational compound.

OTHER EXCLUSIONS

30. Has had an occupation which requires monitoring for radiation exposure, nuclear medicine procedures, or excessive x-rays within the past 3 years.
31. Loss of more than 400 mL blood during the 3 months before screening, eg as a blood donor, or plan to donate blood or blood products in the 3 months after the end of the trial.
32. Unwillingness or inability to follow the procedures outlines in the protocol, including the use of the string bile collection device.
33. History of sensitivity to GSK3640254, or their components thereof, or a history of drug or other allergy that, in the opinion of the investigator or GSK Medical Monitor, contraindicates their participation.

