4.1.1. Screening Period

Participants must be screened within 30 days before the first dose of GSK3640254 and must meet all eligibility criteria.

Treatment Period 1 (oral tablets and ¹⁴C-intravenous infusion)

On Day 1 of Treatment Period 1, after an overnight fast of at least 8 h, each participant will take a single 200 mg oral dose (2 x 100 mg tablets) of GSK3640254 with a moderate fat meal (approximately 600 calories with approximately 30% of calories from fat); the IV infusion of 100 µg of [¹⁴C]-GSK3640254 (approximately 3.7 kBq; 100 nCi) will begin 5 h after oral dose and continue over 1 h. Blood samples, all voided urine, and feces will be collected continuously from Day 1 through Day 8, while duodenal bile will be collected as described below. Participants will be discharged on study Day 8 after completion of the 168-h sample collection and other planned assessments and instructed to return to the clinic on Day -1 of Treatment Period 2.

A non-invasive device (Entero-tracker) to collect duodenal bile will be used in Treatment Period 1. The bile string will be swallowed 2 h after the oral dose and 3 h before the IV infusion starts, a duration recommended to allow transit of the string to the duodenum. Participants will fast from insertion of the bile string until the completion of the IV infusion, at which point a food cue (small standard high-fat meal) will be given to stimulate gall bladder emptying. The Entero-tracker will be removed about 1.5 h after the IV infusion stops (7.5 h after the oral dose).

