6.3. Measures to Minimize Bias: Randomization and Blinding

- This is an open-label study with no randomization and no blinding of participants, site personnel, or sponsor personnel.
- Eligibility will be established during the Screening Period. A cohort of six participants will be admitted to the clinical research unit on the same day and will complete Period 1 and Period 2 on the same schedule with the same study interventions. This approach minimizes potential bias associated with temporal effects.

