6.5. Concomitant Therapy

Any medication or vaccine (including over-the-counter or prescription medicines, vitamins, and/or herbal supplements) that the participant is receiving at the time of enrollment must be discontinued by 15 days before the start of the study intervention. These must be recorded along with:

- reason for use
- dates of administration, including start and end dates
- dosage information, including dose and frequency

The Medical Monitor should be contacted if there are any questions regarding concomitant or prior therapy.

Participants must abstain from taking prescription and non-prescription drugs (including vitamins and dietary and herbal supplements) within 14 days before the start of study intervention until completion of the follow-up visit unless approved by the Investigator in conjunction with a VH/GSK Medical monitor.

Special warnings and precautions for use of GSK3640254 are given in the IB, Section 6.

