8. STUDY ASSESSMENTS AND PROCEDURES

- Study procedures and their timing are summarized in the [SoA](#).
- Protocol waivers or exemptions are not allowed.
- Immediate safety concerns should be discussed with the GSK Medical Monitor immediately upon occurrence or awareness to determine if the participant should continue or discontinue study intervention.
- Adherence to the study design requirements, including those specified in the SoA, is essential and required for study conduct.
- All screening evaluations must be completed and reviewed to confirm that potential participants meet all eligibility criteria. The investigator will maintain a screening log to record details of all participants screened and to confirm eligibility or record reasons for screening failure, as applicable.
- Procedures conducted as part of the participant's routine clinical management and obtained before signing the ICF may be utilized for screening purposes provided the procedure met the protocol-specified criteria and was performed within the time frame defined in the [SoA](#).
- The timing and number of planned study assessments, including safety, and pharmacokinetic assessments may be altered during the study based on newly available data (e.g., to obtain data closer to the time of peak plasma concentrations) to ensure appropriate monitoring.
- The change in timing or addition of time points for any planned study assessments must be documented in a Note to File which is approved by the relevant GSK study team member and then archived in the study sponsor and site study files, but this will not constitute a protocol amendment.
- The IRB/IEC will be informed of any safety issues that require alteration of the safety monitoring scheme or amendment of the ICF.
- The maximum amount of blood collected from each participant over the duration of the study, including any extra assessments that may be required, will not exceed 600 mL.
- Repeat or unscheduled samples may be taken for safety reasons or for technical issues with the samples.

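### Exclusion criterion 31 leaves blood loss between screening and first dose, and donation before the trial ends, uncovered

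*Protocol*

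**What the plan says.** Criterion 31 (protocol section 5.2) has two clauses. One looks back: "Loss of more than 400 mL blood during the 3 months before screening, eg as a blood donor". The other looks forward: "plan to donate blood or blood products in the 3 months after the end of the trial".

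Section 4.1.1 sets the interval between screening and dosing: "Participants must be screened within 30 days before the first dose of GSK3640254". Section 8 caps the blood drawn over the whole study: the total, "including any extra assessments that may be required, will not exceed 600 mL".

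Other criteria in section 5.2 use different reference dates. Criteria 17, 19 and 20 count from first dose and criterion 18 from receipt of study intervention. Criteria 14 and 15 apply at screening or before first dose. Criterion 11 (tobacco and nicotine) counts from screening, but section 5.3.2 then bars use from screening until after the final follow-up visit.

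Criterion 16 excludes for "known or suspected active COVID-19 infection OR contact with an individual with known COVID-19, within 14 days of study enrollment".

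**The concern.** A blood-loss exclusion limits the total a participant loses around a study that takes blood repeatedly. The losses that bear most on this are the latest ones before dosing and any during the study. Criterion 31 reaches neither. The look-back ends at screening and the donation clause begins after the trial has ended, and nothing in the criterion covers the time between.

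At stake is a participant-protection rule that does not reach the weeks closest to sampling. No endpoint or analysis is shown to be affected.

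**Working it through.** There is no sample size, power or alpha figure to reproduce. The check is date arithmetic plus a comparison of sections.

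**Inputs**
- Look-back: 3 months before screening (criterion 31), taken here as 90 days. This is an assumption.
- Screening to first dose: up to 30 days (section 4.1.1).
- Discharge from Period 1 on Day 8, at least 13 days between oral doses, and admission on Day -1 (sections 4.1 and 4.1.1).
- Blood threshold 400 mL (criterion 31); study ceiling 600 mL (section 8).

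**Days uncovered before first dose.** Uncovered days = min(gap from screening to dose, 90).

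| Gap (days) | Uncovered of 90 | Share |
|---|---|---|
| 7 | 7 | 7.8% |
| 14 | 14 | 15.6% |
| 30 | 30 | 33.3% |

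With a 30-day gap the look-back covers days 30 to 120 before dosing, so 90 − 30 = 60 of the last 90 days stay covered. Taking 3 months as 92 days gives 30/92 = 32.6%.

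**Home interval.** If the second oral dose follows 13 days after Day 1, it falls on Day 14 of the Period 1 count, and admission the day before is Day 13. From discharge on Day 8 that is 13 − 8 = 5 days at home, at least. Criterion 31 says nothing about donation in those days, or between discharge from Period 2 and follow-up.

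**Volume.** A loss of more than 400 mL in the gap plus the study maximum gives >400 + 600 = more than 1,000 mL. This is an upper-end illustration, because 600 mL is a ceiling that includes any extra assessments.

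**Does another section close the gap?** Sections 5.3.1 to 5.3.3 cover food and drink, alcohol, tobacco and exercise. Tobacco starts from the same kind of screening anchor, and 5.3.2 carries the restriction through follow-up. There is no matching sentence on blood donation.

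**Criterion 16.** Section 5.4 and the SAP's definition of the Enrolled set (section 4) place enrolment after screening, but neither dates it. If the 14 days are counted back from enrolment, the uncovered days before dosing are about 1 of 14 with enrolment at Day -1 admission, 7 of 14 with enrolment 7 days before dosing, and 14 of 14 with enrolment 14 or more days before. The documents do not say which applies.

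**The case against.** The strongest reply is that a donation rule may sit elsewhere. Inclusion criterion 7 requires compliance with restrictions in the consent form, which was not available here, and neither were the treatment-period schedule tables. Day -1 checks therefore cannot be ruled out, and section 7.2 lets the investigator withdraw a man at any time for safety. It can also be said that reference dates vary throughout section 5.2, that most of the window remains covered, and that the volume illustration adds a hypothetical donation to a ceiling.

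Much of this stands as mitigation. It limits the claim to what criterion 31 and section 5.3 say, and it rules out any statement that such a donation would go unnoticed. It does not change the criterion: an admission check would not by itself make a donation in the gap an exclusion.

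A reader might infer more about COVID-19, and the documents do not support it:
- **A 30-day gap for contact.** Criterion 16 is anchored to enrolment, which follows screening, so the screening interval is not the relevant one.
- **Enrolment at least 15 days before dosing.** Section 6.5 says medication "that the participant is receiving at the time of enrollment must be discontinued by 15 days before the start of the study intervention". That is a concomitant-medication rule and does not define enrolment. The SAP leaves unused reserves out of the Enrolled set, which suggests enrolment nearer admission. Criterion 16's window can also be read in both directions.
- **A need to re-ask criterion 16 before Period 2.** This is a debatable clinical rule that could remove men already dosed with radiolabel. Section 7.1.5 already requires discontinuation for suspect, probable or confirmed infection.
- **Completers falling below 4.** The documents give no rate for this, and the synopsis and sections 4.1 and 9.2 provide for replacement.

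**Conclusion.** The point holds for criterion 31. As written, blood loss of more than 400 mL between screening and first dose does not exclude, and donation in the home interval is not barred. The size is up to 30 of the last 90 days before dosing, at most one third and less if screening is closer to dosing, plus a home interval of at least about 5 days, in a study that may draw up to 600 mL. This rests on 3 months being about 90 days, and on no restriction in the consent form or unseen schedule tables filling the gap.

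A reader might conclude that the safety purpose of the criterion is lost. That goes too far: at least 60 of the 90 days remain covered, so the protection is weakened. For criterion 16, the documents support only that its reference date is undefined, which is a minor clarification.

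**What to change.** In criterion 31, keep the 400 mL and 3-month figures and change two reference periods:
- the look-back to read *from 3 months before screening until the first dose*;
- the donation clause to read *from screening until 3 months after the end of the trial*.

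In criterion 16, state the reference date meant by study enrolment. Which date applies is for the sponsor to decide.

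The cost is a few words in an amendment. The downside is that an occasional volunteer is found ineligible at admission.
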